14. DATA HANDLING AND RECORD KEEPING

EMBER study number

The participants in the study will be assigned a EMBER study number. This number will identify the participant through all stages of data collection and integration.

To reduce errors the EMBER study number will also contain a check digit and it will also be printed as a barcode whenever appropriate, so it can be scanned into data collection tools.

e-CRF data

The EMBER clinical data platform will be built using a bespoke informatics platform (ClinicLE) used previously in respiratory research [18].

Several features of this platform will ensure high quality data collection and integration including:

- user access control so users have permissions to enter/view only appropriate data forms
- integration of data from hospital systems including patient demographics, pathology test results and respiratory physiology
- data field validation (allowing specific types of data; specific ranges of values; or a specific set of selectable options)
- appropriate field design (e.g. using Y/N options instead of checkboxes to ensure the answer is not ambiguous)
- verification through e-signatures and record locking capability
- regular execution of data quality rules to ensure missing/incorrect data is identified quickly
- branching logic so that fields which are not relevant are not displayed to the user
- a form design and data entry audit log/history

A formal test plan will be written during the implementation of the e-CRFs and clarified with other collaborators. Following the completion of the e-CRF implementation, the test plan will be executed to ensure that data collection forms operate within the expected parameters.

A Standard Operating Procedure will be written documenting the use of the EMBER system, specifically for the purpose of entering and managing e-CRF data by the EMBER research staff.

The participants' name and any other identifying detail including date of birth will NOT be included in the final exports of e-CRF data used for research purposes.

Clinical data

Identifiable clinical data exports will be de-identified programmatically by:

- populating the EMBER study number from the recruitment database
- removing hospital numbers, NHS numbers and other patient identifiers
- removing name, address and GP details
- removing or shifting date values
- filtering out free text which may contain identifiable information

Experimental data

Data generated in laboratory experiments will be linked to EMBER study participants using the EMBER study number. No other identifiable data will be present in this data.

Data storage and backup

EMBER clinical data will be stored in an access-controlled database back-end located at the University Hospitals of Leicester. The data will only be available through the hospital network, via the EMBER web

Page 36 of 46

application front-end. The database will be backed up informally every hour to a UHL shared drive in a process managed by the hospital's IT department.

Experimental data and subsequent analyses will be stored using the University of Leicester's research data storage (R) drive backup system (http://www2.le.ac.uk/offices/itservices/ithelp/services/rfs) will be used to maintain all raw experimental data and subsequent analyses.

Risks

Unauthorised access to data: Users will be given appropriate access to databases/data shares for their role, based on recommendations by the PI and other investigators. Identification of research subjects: Research subjects will be identified only through their EMBER study number. The connection between this ID and the patient's demographics will only be available to authorised personnel. Data corruption: In the unlikely event that data becomes corrupted, it will be restored from a backup of the server which is less than 24 hours old. In the case of the EMBER database this means a small amount of data may be missing, and it will have to be re-entered. To mitigate this, paper copies of CRFs should be kept for at least a week after entry into the EMBER clinical data platform. Erroneous data entry: Data entered from paper forms will be verified and if required corrected by a separate person. Data records will then be electronically signed and locked.

EXTERNAL DATA SHARING

Data and samples may be analysed by other investigators/organisations collaborating with the study investigators. In such cases, patient confidentiality will be strictly maintained.

15. STUDY GOVERNANCE

15.1 Clinical Steering Committee (TSC)

The clinical study will be managed through the clinical work package (WP4) of the MRC-EMBER molecular pathology node. The core clinical group ([name], [name], [name] and [name]) all have membership within the EMBER Executive steering group.

The Executive Group comprises the work strand leads and other key Pls. A Scientific Strategy Board comprising all Co-Pls and industrial partners will guide the Executive Board. An operations group chaired by the EMBER's manager will oversee delivery of work. An External Advisory Board with membership derived from experts in the field, Leicester and Loughborough Universities and NHS Research Directors will also oversee the clinical delivery and progress. The Sponsor will be sent minutes from the Scientific Strategy Board and External Advisory Board Meetings. An overview of the governance procedure within EMBER that the clinical work package (WP4) contributes towards is outlined in Figure 6 below.

Review Board MRC/EPSRC Progres **Executive Management Board External Advisory Board Monthly Meetings Annual Meeting** NIHR-DEC Director- [name] European 'breath' experts e.g. [name] (Reutlingen University), [name] (Amsterdam University) RCPath Representative Patient Groups ([name] BLF) + others LU, UoL & NHS Research Directors Progress & Plans [name] [name] [name] [name] [name] [name] Node Manager [name] [name] [name] [name] cientific Strategy Board **Operations Group** 2-Weekly Meetings **Quarterly meeting** Academic Node manager, clinical teams PDRAs, PhD students Board Board WS5 (WS6) WS2 WS3 WS4 WS1

Figure 6: MRC EMBER program management organogram

15.2 Data Safety Monitoring Committee (DSMC)

The operations group within EMBER will report any unexpected serious adverse events to the core clinical group ([name], [name] [name] and [name]). All unexpected SAEs will be discussed by the core clinical group at monthly EMBER executive board meetings.

16.FINANCING AND INSURANCE

Direct Research Costs: Direct research costs required to deliver the stated research: including research staff, technicians, breath sampling, breath analysis and bioinformatics are fully funded by the UK Medical Research Council (MRC) and The Engineering and Physical Sciences Research Council (EPSRC) grant number MR/N005880/1. Additional funding has been received from the Midlands Asthma and Allergy Research Association (MAARA) and the Leicester National Institute for Health Respiratory (NIHR) Biomedical Researh Unit, for the EMBER clinical program.

NHS Treatment Costs: Not applicable for acute research studies as by definition patient care will often continue after the R&D activity has ceased due to the fact that patients will enter chronic care pathways.

NHS Support Costs: None anticipated as the research in question is a discovery biomarker campaign.

Insurance will be provided by the University of Leicester.

Page 38 of 46

APPENDIX A: RECIVA breath sampling device

20. APPENDIX B: RECIVA CE Marking Authorisation

Medicines & Healthcare products Regulatory Agency

Our Ref: CA014968

[name] Owlstone Ltd [name] United Kingdom

29 July 2015

Dear [name],

[name] United Kingdom

www.gov.uk/mhra

MEDICAL DEVICES REGULATIONS 2002: REGULATION 19

Registration of Persons Placing General Medical Devices on the Market

Thank you for informing the Competent Authority of the company's details and for supplying the medical device

Your registration has been recorded based on your declaration that you have determined that the device(s) fall within the definition of "medical device", and that you have classified it/them as falling within Regulation 19 taking into account the intended purpose(s) and mode(s) of action. In accepting your registration, I should make clear that the Competent Authority does not examine each individual notification and therefore cannot and does not necessarily endorse these determinations. Neither does this letter represent any form of accreditation, certification or approval by the UK Competent Authority.

Your registration is based upon your declaration on the RG2 form and means that:

For Manufacturers of Class I medical devices, Assemblers, and Sterilisers

You should now be operating under the Medical Devices Directive and the above Regulations for the products you asked us to register, by fully complying with the essential requirements, CE marking those products or labelling them as such.

For Manufacturers of Custom-made devices and Custom Made Active Implantable

You should be ready to claim compliance with the Directive and Regulations and should be manufacturing custom-made devices in accordance with their requirements.

If you stop placing devices on the market or if you are not complying with the Regulations you should inform us so that we can amend our records. You should be aware that it is an offence to place on the market CE marked devices that do not comply with the regulations.

The information you provided has been recorded against the reference number shown at the top of this letter, which we ask you to quote in all future correspondence and communications.

Please inform us of the following chargable changes:

- the company information e.g. name and address
 additional generic groups of devices (not individual products within an existing generic group)

Please also use the Devices Online Registration Database (DORS) to tell us of the following changes e.g. removal/discontinuation of a device from your registration record, change of contact person, postcode, telephone number and/or email address, for which payment of our statutory fee does not apply. Though, you are required to provide these non-chargeable changes in writing we will not provide an updated letter of

registration. As the updated information does not affect your regulatory obligations or the information published on our Public Access Registration Database (PARD).

Thank you for registering the following generic groups of devices:

Class I Devices:

Sampling And Cell Collection Devices (Patient Contact - Not IVDDs)

Custom Made Devices:

None

Products Covered By Article 12:

Confidentiality

Please note that in accordance with Directive 2007/47/EC as of 21st March 2010 information on the registration of persons responsible for placing devices on the market will no longer be treated as confidential and the Competent Authority will provide third parties with information on the name and address of mandacturers and authorised representatives and their devices that have been registered. However the names of individuals, their telephone numbers and email addresses will remain confidential unless you have chosen to trade using personal details. This change only applies to medical devices and does not affect In Vitro Diagnostic devices registration, which remain confidentiality under Article 19 of the In Vitro Diagnostic Directive 98/79EC.

If your company name or that of a manufacturer that you represent is based on an individual's personal name it will be published unless you inform the MHRA that you would like the company name to remain confidential.

Likewise, if your company address or that of a manufacturer that you represent is the personal home address of an individual it will be published unless you inform the MHRA that you would like the company address to remain confidential.

Should you have any queries regarding your registration please do not hesitate in contacting us.

Yours sincerely

[name]

[name]

[name] [name]

[contact]

21. APPENDIX C: Interim analysis and sample size calculation

21.1 EMBER Sample Size Estimates

An interim analysis was conducted in September 2017 to determine the sample size of the ember acute study.

[figure not shown]
21.2 Closed formula for logistics regression models

82 acutely breathless adults (asthma:35, community acquired pneumonia :16, COPD:26) and 17 healthy controls were utilised for the analysis.

A panel of 10 pre specified aldehyde biomarkers derived from GCMS analysis were supplied. The biomarkers were normalised to a common standard and were not background subtracted.

A closed formula from Hsieh et al, Statis med 1998, was utilised to calculate sample sizes from logistic regression models of the 10 aldehydes with acute breathlessness as the outcome measure. The sample size estimates are also relevant to acute class comparions vs. the sum of other acute classes.

The results of the analyses are outlined in the figure below (each BRI number annotates a specific aldehyde).

Based upon the sample size estimates we would have an 80% power at the 5 % significance level to detect an odds ratio of association of 1.2 for a given disease class with 55 patients per disease class. Given the fact that MRC EMBER seeks to discover and replicate breath VOCs amongst 5 adults classes (CAP, heart failure, COPD, asthma and healthy aged matched subjects).

We would require 110 patients per class – 550 patients across the program to achieve these aims.

Commented [CSB1]: This is not a complete sentence. There is a clause missing, or else the punctuation needs adjustment.

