2. SYNOPSIS

Trial Design Pr	onsor Reference 0569 ospective Acute Care 'Real Life' Observational Study
Trial Participants Pa	
со	tients with acute breathlessness in the following (post-acute pathway nfirmed) strata:
1 * *	Acute Heart failure , characterised by a clinician diagnosis, and a proto-typical sponse to treatment.
re	Community acquired pneumonia , defined as new radiological consolidation sponsive to treatment according to the British Thoracic Society (BTS) mmunity acquired pneumonia guidelines.
wi pr) Adult exacerbations of asthma and COPD, defined as a clinician diagnosis th objective confirmatory evidence of disease based upon historical or ospective measurements, requiring an acute change in treatment (e.g. tibiotics, oral corticosteroids or increased bronchodilator therapy)
(iv) Paediatric exacerbations of acute childhood wheeze and or confirmed asthma
he an wi	Age and/or Home environment matched Adult/Sibling/Parent/Spousal althy volunteers, who have no prior history of asthma, COPD, heart failure d have not been admitted to hospital with community acquired pneumonia thin 6 weeks of the baseline study visit. Additional healthy volunteers will also recruited from local databses.
as) Stable state aged matched participants with a confirmed diagnosis of thma, COPD or heart failure, that have not had and exacerbation of their sease within the preceding 6 weeks.
Planned Sample Size Ar	interim analysis was conducted in September 2017 to determine the sample
siz	e of the ember acute study. Guided by literature search, a panel of 10 pre
sp	ecified aldehyde biomarkers derived from GCMS analysis were supplied. The
bio	omarkers were normalised to a common standard and were not background
su	btracted.
A	closed formula from Hsieh et al, Statis med 1998, was utilised to calculate
sa	mple sizes from logistic regression models of the 10 aldehydes with acute
br	eathlessness as the outcome measure. The sample size estimates are also
re	evant to acute class comparisons vs. the sum of other acute classes.
Ва	sed upon the samples size estimates we would have an 80% power at the 5

	% significance level to detect an odds ratio of association of 1.2 for a given
	disease class with minimum of 55 patients per disease class.

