21.4 Summary

550 patients (110 per class: healthy, acute asthma, acute COPD, community acquired pneumonia, acute heart failure) will be required for combined discovery and replication to (i) detect a minimum odds ratio for association of breath VOCs and acute breathlessness of 1.2 or between acute breathlessness class (e.g. pneumonia with remaining categories as a reference).

Page 45 of 46

This sample size and group allocation will give us sufficient power to discover a disease specific VOC over a 95% CI with a specificity of 80% \pm 8%, sensitivity of 80% \pm 8% at an α = 0.05. The sample size will give us sufficient power to replicate based upon biomarker sensitivity but not specificity.

The power calculation assume that ALL acute patients have one or more of the following (i) patient defined acute breathlessness or (ii) a unit change in eMRC (assuming that they can quantify their usual baseline eMRC).

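### The claim of 80% power for an odds ratio of 1.2 with 55 per class does not hold for breath VOCs in general: per SD, power is about 22–23% per phase

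*Protocol*

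**What the plan says.** Section 21.2 (Appendix C) describes a pilot analysis: "82 acutely breathless adults (asthma:35, community acquired pneumonia :16, COPD:26) and 17 healthy controls were utilised for the analysis". On the markers it says "A panel of 10 pre specified aldehyde biomarkers derived from GCMS analysis were supplied". A closed formula for logistic regression was applied, and the protocol concludes that there is 80% power at the 5% level "to detect an odds ratio of association of 1.2 for a given disease class with 55 patients per disease class". It adds: "The sample size estimates are also relevant to acute class comparions vs. the sum of other acute classes". The programme total follows from this: "We would require 110 patients per class – 550 patients across the program to achieve these aims".

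The synopsis repeats the power claim for a given "disease class with minimum of 55 patients per disease class". Section 21.4 then says that 550 patients will "detect a minimum odds ratio for association of breath VOCs and acute breathlessness of 1.2 or between acute breathlessness class". That sentence no longer refers to the ten aldehydes.

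The readable text gives no unit for the odds ratio and no marker SD. Section 21.2 points to a figure for the individual results ("The results of the analyses are outlined in the figure below (each BRI number annotates a specific aldehyde"), which was not available to us.

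**The concern.** An odds ratio for a continuous marker has no defined power until its unit and the marker's spread are stated. At a fixed sample size, an odds ratio of 1.2 per raw unit gives high power for a marker with a large SD and very low power for one with a small SD. A single figure of 1.2 therefore cannot be the detectable effect for VOCs as a group, least of all in a study meant to discover new ones. An odds ratio of 1.2 per SD is also a small effect, and 55 per class looks far too few to detect it with 80% power.

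The claim is the headline power statement in the synopsis and Appendix C, and 110 per class and 550 in total are derived from it. A reader who takes 1.2 as detectable for any VOC could read a null result, or a failed replication, as evidence against associations that each phase would usually miss.

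**Working it through.** **Inputs**
- Five adult classes of 55 per phase, so n = 275 per phase and 550 over both phases (sections 21.2, 21.4, 21.5).
- 80% acute and 20% healthy, with equal class sizes (section 21.3).
- Contrasts: healthy against acute, or one class against all others, P = 0.2 (equivalently 0.8); one acute class against the other three, 55 of 220, P = 0.25.
- 5% level (section 10.3). Sidedness is not stated, so two-sided is assumed and one-sided is also shown.
- ln 1.2 = 0.1823; z-values 1.960 + 0.8416 = 2.8016.

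**Formulae** (closed formula for logistic regression with a continuous covariate)
- Power = Φ(SD × 0.1823 × √[nP(1−P)] − 1.96), plus the negligible opposite tail.
- N for 80% power = 2.8016² / [P(1−P) × (SD × 0.1823)²].
- Detectable odds ratio per SD = exp(2.8016 / √[nP(1−P)]).
- SD needed if 1.2 is per raw unit = ln(detectable odds ratio) / 0.1823.

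**Trying to reproduce the 80%, odds ratio per 1 SD**

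For n = 275, P = 0.2: nP(1−P) = 44, √44 = 6.633, and 0.1823 × 6.633 = 1.209. Power = Φ(1.209 − 1.96) plus the other tail = 22.7%. N for 80% = 7.849 / (0.16 × 0.03324) ≈ 1,476.

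For n = 220, P = 0.25: nP(1−P) = 41.25, √41.25 = 6.423, and 0.1823 × 6.423 = 1.171. Power = 21.6%. N for 80% = 7.849 / (0.1875 × 0.03324) ≈ 1,260.

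| Setting | Two-sided power | One-sided power | Detectable OR per SD (80%, two-sided) | Raw-unit SD needed for OR 1.2 |
|---|---|---|---|---|
| Per phase, n = 275, P = 0.2 | 22.7% | 33.2% | 1.53 | 2.32 |
| Per phase, n = 220, P = 0.25 | 21.6% | 31.8% | 1.55 | 2.39 |
| Both phases pooled, n = 550, P = 0.2 | 40.2% | 52.6% | 1.35 | 1.64 |
| Both phases pooled, n = 440, P = 0.25 | 38.1% | 50.5% | 1.36 | 1.69 |

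**Other readings, still per SD and two-sided**
- Pilot's own acute share (82/99), n = 275: 20.7%.
- 55 against 55: about 16%.
- Upper recruitment ranges from the synopsis, discovery phase (400 acute, 150 healthy): 35% (100 of 400 acute), 38% (100 of 550) and 48% (150 healthy of 550).
- Upper ranges pooled over both phases (800 acute, 225 healthy): 61%, 64% and 68%. One-sided, these become 72%, 75% and 78%.

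No per-SD reading reaches 80%.

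**Odds ratio per raw unit, n = 275, P = 0.2**

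| Marker SD (raw units) | 0.5 | 1 | 1.5 | 2 | 2.32 |
|---|---|---|---|---|---|
| Power | 9% | 23% | 44% | 68% | 80% |

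At SD 2.32 the acute-class contrast has 77.5%, so the two named contrasts behave alike.

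**Check without the closed formula.** Repeated simulations of logistic fits with a normal marker of SD 1 gave 22–24% (n = 275) and 20–22% (n = 220) for an odds ratio of 1.2. They gave 79–80% for 1.53 at n = 275 and 77–80% for 1.55 at n = 220.

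**The case against.** The strongest reply is that the calculation in dispute sits in a figure lost in PDF reading. That figure may give the unit and the SD for each aldehyde, and a marker with a raw-unit SD of about 2.3 or more would have the stated 80%. The text nowhere says that the odds ratio is per SD, and normalising to a common standard does not imply SD 1. This stands: the 80% may be right for some of the ten aldehydes, and the absence of the figure is not held against the plan. It does not rescue section 21.4, because results for ten named aldehydes cannot fix the detectable effect for VOCs with other SDs.

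A second reply is that section 21.4 only summarises 21.2 and is loosely worded. But neither it nor the synopsis states a unit or carries any limit to particular markers, so the reader cannot recover one. It is also fair to say that 110 per class is probably a head-count of two phases rather than a pooled test. The pooled figures are given only as the more favourable reading, and they also fall short.

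Third, section 10.2 calls the study exploratory and gives a separate basis of 20 events per variable, section 21.3 adds a precision calculation, and section 10.6 plans to recalculate the replication numbers after discovery. No decision rule uses 1.2. These points limit the harm, and they are why no change in patient numbers is proposed. They do not make the stated figure correct.

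**Conclusion.** The concern holds for the claim as it is worded and extended. Read per SD, 55 per class gives 22–23% two-sided power per phase rather than 80%, so each phase would miss a true odds ratio of 1.2 more than three times in four. Read per raw unit, the 80% applies only to markers with an SD of about 2.3–2.4 units or more.

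This rests on a continuous marker, a two-sided 5% test, equal classes of 55, a single-marker model and no adjustment for testing several markers. One-sided testing raises the per-phase figure only to 32–33%. Bonferroni over ten aldehydes would lower it to about 5–6%. The finding does not show that the unseen per-aldehyde calculation is wrong, nor that the study should not be run. The statement should be corrected; the design can stand.

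**What to change.** Keep the patient numbers and change the wording in the synopsis, 21.2 and 21.4 in one of two ways, according to what the calculation used.

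1. State the odds ratio per 1 SD of the marker and replace 1.2 with the value detectable at 80% power and two-sided 5% with 55 per class per phase: about 1.53 for one class against the rest or healthy against acute, and about 1.55 for one acute class against the other acute classes.
2. If 1.2 was per raw unit, state the unit and the SD (or refer to the figure if it gives them), limit the claim to the aldehydes and contrasts for which it holds, and remove the extension to breath VOCs in general from 21.4.

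The cost is wording in three places, with no extra patients or procedures. The downside is that the stated detectable effect becomes less favourable under the first option, or covers fewer markers under the second.
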